## **2.6 Analysis of the key secondary objective**

Not applicable.

### **2.6.1 Key secondary endpoint**

Not applicable.

### **2.6.2 Statistical hypothesis, model, and method of analysis**

Not applicable.

### **2.6.3 Handling of missing values/censoring/discontinuations**

Not applicable.

## **2.7 Analysis of secondary efficacy objective(s)**

Refer to [Section 1.2](#) for the list of secondary objectives.

### **2.7.1 Secondary endpoints**

The secondary efficacy variables are the following (see [Section 2.11](#) for details of the assessments from which the efficacy variables are derived):

1. Reduction in ASDAS  $\geq 1.1$  from Week 16 (yes, no)
2. Change from Week 16 in total BASDAI
3. BASDAI50 response (yes, no)
4. ASAS20 response (yes, no)
5. ASAS40 response (yes, no)
6. ASAS partial remission (yes, no)
7. Change from Week 16 in ASAS-Health Index

## 8. Change from Week 16 in FACIT-Fatigue

### 2.7.2 Statistical hypothesis, model, and method of analysis

Analyses of the secondary efficacy variables will be based on the Full Analysis Set.

#### Reduction in ASDAS $\geq 1.1$ from Week 16

Reduction in ASDAS  $\geq 1.1$  from Week 16 (yes, no) will be analyzed at each time point in Treatment Period 2 until Week 52 using a logistic regression model with treatment, TNF-alpha inhibitor status (naive, inadequate responder), and Week 16 body weight as explanatory variables. The odds ratios and 95% confidence intervals for the odds ratios will be reported, based on the fitted model. Similar analysis will be performed for the subgroups defined by TNF-alpha inhibitor status.

A 95% confidence interval for the difference, at each time point in Treatment Period 2 until Week 52, between the two treatment groups in the proportion of patients who have reduction in ASDAS  $\geq 1.1$  from Week 16 will be calculated using the normal approximation to the binomial distribution for the Full Analysis Set.

Number and percentages of patients with reduction in ASDAS  $\geq 1.1$  from Week 16 will also be reported for each treatment group in each treatment period by visit and similarly by TNF-alpha inhibitor status (naive, inadequate responder).

#### Change from Week 16 in total BASDAI

Analysis of change from Week 16 in total BASDAI score will be performed using mixed-effects model repeated measures (MMRM) with treatment, visit, and TNF-alpha inhibitor status (naive, inadequate responder) as factors, Week 16 score and Week 16 weight as covariates, and treatment-by-visit and Week 16-by-visit as interaction terms (Diggle, Heagerty, and Liang KY, 2002). The least-squares (LS) mean difference between secukinumab 150 mg - 300mg (IR) and secukinumab 150 mg - 150mg (IR) will be presented along with the corresponding 95% CI.

Similar analysis will be performed for the subgroups defined by TNF-alpha inhibitor status.

Descriptive summary statistics for change from baseline in Treatment Period 1 and change from Week 16 in Treatment Period 2, for total BASDAI score for each visit will be provided. Similarly, descriptive summary statistics will also be provided by TNF-alpha inhibitor status.

Analysis of change from Week 16 in **ASAS-Health Index** and change from Week 16 in **FACIT-Fatigue** will be similar to analyses as described for change from Week 16 in total BASDAI.

Analysis of **BASDAI50 response**, **ASAS20 response**, **ASAS40 response**, and **ASAS partial remission** will be similar to the analyses as described for reduction in ASDAS  $\geq 1.1$  from Week 16.

Also summary statistics for secondary efficacy variables 1, 2, 4 and 5 for the patients in Treatment Period 1 who entered Treatment Period 2 will be provided based on the below criteria :

- Patients receiving 150mg (open label) (Enrolled Set)
- Patients receiving randomized 300mg and 150mg (Randomized Set)

- Patients who are responders (Responder Set)
- Patients who are nonresponders (Nonresponder Set)

In addition, the above analysis will be done by TNF-alpha inhibitor status and by visit.

As additional analyses, following will be performed on Full Analysis Set:

1. Descriptive summary statistics for change from baseline (Week 0) to all visits in Treatment Period 2 for secondary efficacy variables - total BASDAI, ASAS-Health Index and FACIT-Fatigue, will be provided.
2. Number and percentages of patients for secondary efficacy variables 3 - 6 will also be reported for each treatment group considering baseline (Week 0) to derive the response for Treatment Period 2 and similarly by TNF-alpha inhibitor status only for ASAS20 and ASAS40 response.
3. Line plots of mean change from baseline for secondary efficacy variables – total BASDAI, ASAS-Health Index and FACIT-Fatigue, and line plots displaying responder percentage for secondary efficacy variables 3 – 6, for entire treatment period will be presented from Week 1 to Week 52, considering baseline as Week 0.
4. Descriptive summary statistics for change from baseline (Week 0) in all 6 components of BASDAI will be provided in Treatment Period 1 and 2. Line plots of mean change from baseline (Week 0) for these components will also be presented over entire treatment period (from Week 1 to Week 52).

### **2.7.3 Handling of missing values/censoring/discontinuations**

For secondary efficacy variables 1 and 3 – 6, patients who discontinue prematurely for any reason will be considered nonresponders from the time they discontinued through to Week 52. Also, patients who do not have the required data to compute response (e.g., ASAS components) at the specific time point will be classified as nonresponders.

Secondary efficacy variables 2, 7, and 8, will be analyzed using a mixed-effects model repeated measures (MMRM) which is valid under the missing at random (MAR) assumption. For analyses of these variables, if all post-baseline values are missing then these missing values will not be imputed and the patient will be removed from the analysis of the corresponding variable, i.e., it may be that the number of patients providing data to an analysis is smaller than the number of patients in the FAS.

## **2.8 Safety analyses**

The safety analysis will be performed on Enrolled Set for Treatment Period 1 and on Safety Set for Treatment Period 2.

All listings and tables will be presented for Treatment Period 1, for responders who enter Treatment Period 2, and by treatment group for inadequate responders who are randomized.

The analyses for treatment-emergent adverse events, serious adverse events and risk based on adverse events will be summarized. Safety analyses will be performed on treatment received or actual treatment as described below:

- The actual treatment or treatment received for summaries of safety data will differ from the treatment assigned at randomization only if a subject received the wrong treatment during the entire study.
- For those patients who received not the treatment randomized, i.e., who received erroneously the wrong treatment at least once, an additional AE listing will be prepared displaying which events occurred after the treatment errors.

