5.2 Treatment arms

Treatment Period 1

Once screening has been completed and patients have met the eligibility criteria, all patients will undergo 16 weeks of open-label treatment with secukinumab 150 mg s.c. self-administered at the site at baseline, Weeks 1, 2, 3, 4, 8, and 12.

All assessments at the scheduled visit will be performed before the patients receive the injection with the appropriate study medication for that visit.

At Week 12 and Week 16, all patients will be assessed for achieving the ASDAS inactive disease (<1.3) status, as well as for an inadequate response or a non-response. Patients will then be divided into three groups:

1. **Responders:** Patients achieving ASDAS inactive disease (total score < 1.3) status at Week 12 and Week 16 and who do achieve a decrease (improvement) from baseline in total ASDAS score at both Week 12 and Week 16.
2. **Inadequate responders:** Patients who have active disease, defined as an ASDAS total score of ≥ 1.3 at either Week 12 or Week 16, and who do achieve a decrease (improvement) from baseline in total ASDAS score at both Week 12 and Week 16.
3. **Non-responders:** Patients who exhibit no change or an increase (worsening) from baseline in total ASDAS score at either Week 12 or Week 16

Treatment Period 2 (Responders and Non-responders)

Responders: Patients achieving responder status will enter Treatment Period 2 and continue to receive 150 mg s.c. (one s.c. injection of secukinumab 150 mg) at Weeks 16, 20, 24, 28, 32, 36, 40, 44, and 48, as well as one matched placebo dose (s.c. injection) to maintain the integrity of the blind for the randomized Inadequate Responder group. This Responder group will be evaluated for maintenance of ASDAS inactive disease while remaining on 150 mg of secukinumab. All assessments at the scheduled visit will be performed before the patients receive the injection with the appropriate study medication for that visit.

NOTE: To minimize patient burden, at the Week 16 visit, the hs-CRP measurement that is part of the ASDAS calculation will be imputed from the Week 12 hs-CRP results to allow for assignment into the groups above. Historically, hs-CRP levels have varied little between Week 12 and Week 16 in previous studies of secukinumab in active AS.

Non-responders: Nonresponders will terminate the study at Week 16.

Treatment Period 2 (Inadequate Responders)

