Inadequate responders will be randomized via the Interactive Response Technology (IRT) system in a 1:1 ratio to receive either secukinumab 300 mg (two s.c. injections of the 150 mg dose) or secukinumab 150 mg (one s.c. injection of the 150 mg dose and one s.c. injection of placebo) at Weeks 16, 20, 24, 28, 32, 36, 40, 44, and 48.

Patients will self-administer all secukinumab doses up to Week 48 after they have received training by the site to self-administer their secukinumab dose. While patients are encouraged to self-inject, continued assistance by the site or home nurse is acceptable. All assessments at the scheduled visit will be performed before the patients receive the injection with the appropriate study medication for that visit.

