## 1.1 Study design

This study will use a randomized, double-blind, parallel-group, multicenter design.

There are 3 study periods:

1. **Screening:** A screening period will take place over two separate visits, with the first visit used to assess eligibility and to washout prohibited medications (up to 11 weeks). The second screening visit, which will occur at a minimum of 2 weeks prior to the baseline visit for all patients.

**Note: Patients that do not require a washout, and who satisfy all inclusion and none of the exclusion criteria at the first screening visit can initiate the second screening visit one week after their first screening visit.**

2. **Treatment Period 1:** Patients who meet all of the inclusion criteria and none of the exclusion criteria will have a Baseline Visit performed to start Treatment Period 1. During this 16-week period, all patients will receive open-label secukinumab 150 mg [1 x 1.0mL s.c.] at baseline, Weeks 1, 2, 3, 4, 8, and 12. At Week 16, patients will be placed into one of the following groups:
  - a. **Responders:** Patients achieving ASDAS inactive disease (total score < 1.3) at **both** Week 12 and Week 16 and who do achieve a decrease (improvement) from baseline in total ASDAS score at both Week 12 and Week 16.
  - b. **Inadequate responders:** Patients who have active disease, defined as an ASDAS total score of  $\geq 1.3$  at either Week 12 or Week 16, and who do achieve a decrease (improvement) from baseline in total ASDAS score at both Week 12 and Week 16.
  - c. **Non-responders:** Patients who exhibit no change or an increase (worsening) from baseline in total ASDAS score at **either** Week 12 **or** Week 16

**Note:** To minimize patient burden, at the Week 16 visit, the hs-CRP measurement that is part of the ASDAS calculation will be imputed from the Week 12 hs-CRP results to allow for assignment into the groups above. Historically, hs-CRP levels have varied little between Week 12 and Week 16 or in previous studies of secukinumab in active AS.

[figure not shown]
3. **Treatment Period 2:** Upon completion of the Week 16 visit,

- a. **Responders** will enter Treatment Period 2 and continue to receive secukinumab 150 mg every 4 weeks through Week 48 as well as one matched placebo dose (s.c. injection) to maintain the integrity of the blind for the randomized Inadequate Responder group.

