## 2.2 Analysis sets

The following analysis sets will be used for the statistical reporting and analyses:

**Enrolled Set:** The Enrolled Set consists of all enrolled patients for the initial 16-week, Treatment Period 1.

Note: For safety analyses, the Enrolled Set will consist of enrolled patients for the initial 16-week, Treatment Period 1 who received at least one dose of the open-label treatment, secukinumab 150 mg.

**Responder Set:** The Responder Set consists of all patients who are labeled as responders at the end of Treatment Period 1, and enter Treatment Period 2 receiving blinded secukinumab 150 mg every 4 weeks through Week 48.

**Safety Set:** The Safety Set includes all patients who received at least one dose of study treatment during Treatment Period 2. Patients will be analyzed according to the study treatment received.

**Full Analysis Set:** The Full Analysis Set comprises all patients to whom study treatment has been assigned by randomization. According to the intent-to-treat principle, patients will be analyzed according to the treatment they have been assigned to during the randomization procedure.

**Non-responder Set:** The Non responder Set consists of all patients who are labeled as non-responders at the end of Treatment Period 1 and do not enter Treatment Period 2.

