## **2.4 Treatments (study treatment, rescue medication, concomitant therapies, compliance)**

### **2.4.1 Study treatment / compliance**

#### **Study Treatment**

The summaries by treatment group will be performed by the actual treatment received (as follows) for every visit until Week 16.

Treatment groups in Treatment Period 1:

- Secukinumab 150 mg

In Treatment Period 2, the summaries by treatment group will be performed by the actual treatment received (as follows) for every visit up to Week 52, including patients who switched at Weeks 16.

Treatment groups in Treatment Period 2:

- Secukinumab 150 mg - 300 mg (IR)
- Secukinumab 150 mg - 150 mg (IR)
- Secukinumab 150 mg – 150 mg (R)

where, R: Responders and IR: Inadequate Responders

Treatment groups in entire treatment period:

- Secukinumab 150 mg

- Secukinumab 300 mg

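### SAP 2.8 ties reassignment in the safety tables to the whole study, so a patient randomised to 150 mg but given 300 mg throughout Treatment Period 2 would stay under 150 mg

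*SAP*

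**What the plan says.** The Safety Set is defined by dosing after Week 16: "The Safety Set includes all patients who received at least one dose of study treatment during Treatment Period 2". SAP 2.2 then sets the principle: "Patients will be analyzed according to the study treatment received". Protocol 9.1 defines the set in the same way.

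SAP 2.4.1 repeats the principle for Treatment Period 2: "the summaries by treatment group will be performed by the actual treatment received (as follows) for every visit up to Week 52". The groups it lists are the two randomised sequences and the responders.

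SAP 2.8 turns the principle into a derivation rule. Received treatment departs from assigned treatment "only if a subject received the wrong treatment during the entire study". For lesser errors it adds a listing and moves nobody: for those "who received erroneously the wrong treatment at least once, an additional AE listing will be prepared", showing the events that followed the error.

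On dosing, SAP 1.1 states that before randomisation "all patients will receive open-label secukinumab 150 mg [1 x 1.0mL s.c.] at baseline, Weeks 1, 2, 3, 4, 8, and 12", and Protocol 5.2 likewise says "all patients will undergo 16 weeks of open-label treatment with secukinumab 150 mg". After randomisation Protocol 5.2 schedules doses "at Weeks 16, 20, 24, 28, 32, 36, 40, 44, and 48".

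**The concern.** The rule in SAP 2.8 reads like one written for a trial randomised at first dose. Here randomisation comes at Week 16, after an open-label period in which everyone is meant to receive 150 mg. If the condition covers the whole study, the correctly given open-label doses count against reassignment. A patient who received the other arm's dose at every randomised visit would then remain in the assigned arm's column.

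Safety and tolerability is a stated objective, and the randomised contrast is between two doses. The adverse event, laboratory and vital sign tables are meant to show each dose as given. On the literal text, a patient treated wholly with 300 mg after randomisation could be counted under 150 mg.

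**Working it through.** The plan states no figure for this point, so the check is a count of doses and a reading of the rule.

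**Inputs**
- Dosing visits in Treatment Period 1 (SAP 1.1): baseline and Weeks 1, 2, 3, 4, 8, 12 = 7.
- Dosing visits in Treatment Period 2 (Protocol 5.2): Weeks 16, 20, 24, 28, 32, 36, 40, 44, 48 = 9.
- Total: 7 + 9 = 16.
- Planned patients per randomised arm (Protocol 9.8, SAP 3): 97.

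**What the entire study covers.** SAP 2.1.1 defines the on-treatment phase as 52 weeks, which includes the open-label period. SAP 2.5.2 and 2.7.2 use the entire treatment period to mean Week 1 to Week 52. The SAP's own use of the word therefore spans both periods.

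**The rule applied.** Take a patient randomised to 150 mg who completes all visits, has Period 1 given as planned, and receives 300 mg at *k* of the 9 later visits.

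| k wrong in Period 2 | Wrong share of all 16 | Literal rule (16 of 16 wrong) | Period 2 rule (9 of 9 wrong) |
|---|---|---|---|
| 0 | 0% | stays | stays |
| 1 | 6.25% | stays | stays |
| 5 | 31.25% | stays | stays |
| 8 | 50% | stays | stays |
| 9 | 56.25% | stays | moved to 300 mg |

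The literal condition fails for every *k* from 0 to 9. The two readings part only at *k* = 9, where the as-received principle plainly calls for a move.

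**Early discontinuation.** One Period 2 dose is enough for the Safety Set. If that single dose was wrong, 1 of 7 + 1 = 8 doses is wrong (12.5%), so the literal rule leaves the patient in place. A rule on administrations received in Period 2 gives 1 of 1 and moves the patient.

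**The other direction.** A patient randomised to 300 mg who only ever received 150 mg never had the assigned dose. A programmer might reassign that patient, but only by calling the planned open-label doses wrong. The text is therefore insecure in this direction, whereas for a patient randomised to 150 mg it is clear and gives the wrong result.

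**Size per patient.** 1/97 = 1.03 percentage points, if the misplaced patient had the event. As an illustration, take 2 of 97 under 150 mg and 1 of 97 under 300 mg (2.06% and 1.03%). Moving one patient with the event gives 1/96 = 1.04% and 2/98 = 2.04%, so the order reverses. Counts this small are uninformative about dose in either arrangement.

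**The case against.** The strongest reply concerns intent. The sentence in SAP 2.8 compares treatment received with treatment assigned at randomisation, and nothing is assigned that way before Week 16. The Safety Set is itself defined by Period 2 dosing. On that view, wrong can only mean wrong against the randomised arm, and the condition means throughout the randomised period. The patient with nine wrong doses would then be moved. This is probably what was intended, but it has to be inferred, and the SAP's use of entire elsewhere points the other way.

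It can also be said that SAP 2.8 does not contradict SAP 2.2 but supplies its working definition. That holds as to structure. It does not rescue a definition that, read as written, places a patient under a dose never received as intended after randomisation. SAP 2.4.1 sits under study treatment and compliance and does not clearly govern the adverse event tables. It still needs to use the same rule, or exposure and events for one patient could fall in different columns.

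Three further points stand. The additional listing already deals with isolated errors, and whether one wrong dose in nine should move a patient is a matter of convention. The deviations in SAP 5.5 for incorrect stock and for extra injections do not establish wrong-arm dosing: their code governs inclusion in analysis sets, not the treatment column. Finally, dispensing by medication number at each visit makes sustained wrong-arm dosing unlikely.

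**Conclusion.** The point holds as a wording error in a stated rule. Read literally, SAP 2.8 cannot move a patient randomised to 150 mg who received 300 mg at every Period 2 dose, and that result is at odds with the as-received principle in Protocol 9.1, SAP 2.2 and SAP 2.4.1. This assumes that Period 1 was given as planned and that the entire study has its ordinary meaning.

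The effect on results is unknown. The documents do not say how many patients, if any, were dosed wrongly throughout Period 2. If there were none, every table is unchanged. Otherwise the effect is about 1 percentage point per misplaced patient with the event, at planned numbers.

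A reader might infer more on two counts, and the documents do not support either. The first is that nobody could ever be reassigned, so that the safety analysis is simply as randomised; the likely intent and the possible handling of a 300 mg patient who only received 150 mg stand against that. The second is that a dose effect is being hidden; the safety summaries are descriptive, with no test between doses, and no misplaced patient is shown to exist. The rule does not address responders, who are not randomised.

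**What to change.** In SAP 2.8, replace the reference to the entire study with: *at every study treatment administration received in Treatment Period 2*. Have SAP 2.2 and 2.4.1 refer to that rule, so that exposure, adverse events, laboratory values and vital signs use one derived treatment variable. Keep the additional adverse event listing for patients with any wrong dose. Record the clarification in SAP section 4, which does not at present mention the narrower rule in 2.8.

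The cost is one phrase, two cross-references and a check of one derived variable.

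A different threshold for patients with a mixture of doses, such as the majority of administrations, is optional. The SAP's latest listed update is after database lock, and Protocol 8.3 releases treatment codes after lock. Any such threshold should therefore be fixed without knowledge of outcomes by treatment. The period correction only makes the rule match the principle already stated.

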### 2.8.1 Adverse events (AEs)

The crude incidence of treatment emergent adverse events (TEAEs) will be summarized by primary system organ class (SOC) and preferred term (PT) for Treatment Period 1 and Treatment Period 2.

Treatment-emergent adverse events (TEAEs) are defined as follows:

- For Treatment Period 1, TEAEs are those AEs that started on or after the first dose date of study treatment, or events present prior to the first dose date of study treatment but increased in severity based on preferred term and the earlier of the last dose date in Treatment Period 1 + 84 days or prior to the first dose date in Treatment Period 2.
- For Treatment Period 2, TEAEs are those AEs that started on or after the first dose date of study treatment in Treatment Period 2 and on or before the last dose date + 84 days.

In addition, exposure time-adjusted rates (incidence rate) including 95% confidence intervals will be provided for entire treatment period to adjust for differences in exposure. For the entire treatment period, TEAEs are those AEs that started on or after the first dose of study treatment, or events present prior to the first dose of study treatment but increased in severity based on preferred term and on or before last dose date + 84 days. For summaries over the entire treatment period, patients who switched from secukinumab 150 mg to secukinumab 300 mg will appear in both treatment groups.

Crude incidence rates and exposure-adjusted incidence rates will be graphically presented for all TEAEs and serious TEAEs along with 95% confidence intervals, by system organ class.

Adverse events will be summarized by presenting, for each treatment group, the number and percentage of patients having at least one AE, having an AE in each primary system organ class and having each individual AE (preferred term). Summaries (crude incidences only) will also be presented for AEs by severity and for study treatment related AEs. If a particular AE 'severity' is missing, this variable will be listed as missing and treated as missing in summaries. If a subject reported more than one adverse event with the same preferred term, the adverse event with the greatest severity will be presented. If a subject reported more than one adverse

event within the same primary system organ class, the subject will be counted only once with the greatest severity at the system organ class level, where applicable.

Separate summaries will be provided for

- adverse events suspected to be related to study drug by the investigator
- deaths
- serious adverse events
- adverse events leading to discontinuation

A listing of non-treatment emergent adverse events will be provided. These adverse events occurred before the first dose of the study treatment. The crude incidence rate will be provided without treatment information.

Algorithms for date imputations will be provided in Programming Specifications.

For SAEs that occur during screening, a listing will be prepared for all patients screened including screening failures.

A listing of suspected or confirmed SARS-CoV-2 infections will be provided.

For legal requirements of ClinicalTrials.gov, two required tables on TEAEs which are not SAEs with an incidence greater than or equal to 5% and on treatment-emergent SAEs and SAEs suspected to be related to study treatment will be provided by SOC and PT for entire treatment period.

If, for the same patient, several consecutive TEAEs (irrespective of study treatment causality, seriousness and severity) occurred with the same SOC and PT:

- A single occurrence will be counted if there is  $\leq 1$  day gap between the end date of the preceding AE and the start date of the consecutive AE.
- More than one occurrence will be counted if there is  $> 1$  day gap between the end date of the preceding AE and the start date of the consecutive AE.

For occurrence, the presence of at least one SAE / SAE suspected to be related to study treatment / non SAE has to be checked in a block, e.g., among AEs in a  $\leq 1$  day gap block, if at least one SAE is occurring, then one occurrence is calculated for that SAE.

The number of deaths resulting from SAEs suspected to be related to study treatment and SAEs irrespective of study treatment relationship will be provided by SOC and PT.

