9.5.2 Safety variables

For safety analyses, the Enrolled Set will be used for Treatment Period 1, and the Safety Set will be used for Treatment Period 2. All listings and tables will be presented for Treatment Period 1, for responders who enter Treatment Period 2, and by treatment group for inadequate responders who are randomized.

Adverse events

All information obtained on adverse events will be displayed by treatment group and patient.

The number (and percentage) of patients with adverse events will be summarized in the following ways:

by treatment, primary system organ class and preferred term;

by treatment, primary system organ class, preferred term and maximum severity;

by treatment, Standardized MedDRA Query (SMQ) and preferred term.

Separate summaries will be provided for study medication related adverse events, death, serious adverse events, and other significant adverse events leading to discontinuation.

A patient with multiple adverse events within a primary system organ class is only counted once towards the total of the primary system organ class.

Vital signs

All vital signs data will be listed by treatment group, patient, and visit/time, and if ranges are available, abnormalities will be flagged. Summary statistics will be provided by treatment and visit/time.

12-lead ECG

All ECG data will be listed by treatment group, patient and visit/time; abnormalities will be flagged. Summary statistics will be provided by treatment and visit/time.

Clinical laboratory evaluations

All laboratory data will be listed by treatment group, patient, and visit/time, and if reference ranges are available, abnormalities will be flagged. Summary statistics will be provided by treatment and visit/time.

[REDACTED]

[REDACTED]

[REDACTED]

[REDACTED]

[REDACTED]

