### Baseline and post-baseline definitions

In general, a baseline value refers to the last measurement available prior to administration of the first dose of study treatment. A post-baseline value refers to a measurement taken after the first dose of study treatment.

For Treatment Period 2, Week 16 assessments will be considered the baseline for all analyses performed during this period.

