### 2.8.3 Laboratory data

The summary of laboratory evaluations will be presented for three groups of laboratory tests (hematology, chemistry and urinalysis).

Descriptive summary statistics for the change from baseline in Treatment Period 1 and change from Week 16 in Treatment Period 2 to each study visit in respective treatment periods will be presented. These descriptive summaries will be presented by laboratory test and treatment group. Change from baseline (or Week 16) will only be summarized for patients with both baseline (or Week 16) and post-baseline (or post-Week 16) values and will be calculated as:

$$\text{change from baseline} = \text{post-baseline value} - \text{baseline value}$$

$$\text{change from Week 16} = \text{post-Week 16 value} - \text{Week 16 value}$$

For urinalysis and urine pregnancy test, data will be listed by treatment and patient.

QuantiFERON TB-Gold test, serum pregnancy test results and HLA-B27 results will be listed at Screening Visit 2, by treatment and patient.

Shift table will be provided for all laboratory variables to compare a patient's baseline laboratory evaluation relative to observed post-baseline values in Treatment Period 1. The reference laboratory ranges will be used to evaluate whether a particular laboratory test value was within reference range, low, or high for each visit value relative to whether or not the baseline value was within reference range, low, or high. The shifts to the most extreme laboratory test value within the treatment period will be presented (including category "high and low"). These summaries will be presented by laboratory test and treatment group. Similar shift tables will be provided for all laboratory variables to compare a patient's Week 16 laboratory evaluation relative to observed post-Week 16 values in Treatment Period 2.

The following laboratory variables will be analyzed with respect to numerical common terminology criteria for adverse events (CTCAE) grades, given in [Table 2-3](#): hemoglobin (HGB), platelets, white blood cell (WBC) count, neutrophils, lymphocytes, creatinine, total bilirubin (TBL), gamma-glutamyl transferase (GGT), alanine aminotransferase (ALT), aspartate aminotransferase (AST), alkaline phosphatase (ALP), glucose.

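### Does the Period 2 adverse-event definition lose events that worsen after randomisation?

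*SAP*

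**What the plan says.** SAP section 2.8.1 sets out three definitions.

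- **Period 1:** events that start on or after the first dose, plus "events present prior to the first dose date of study treatment but increased in severity based on preferred term". The window closes at the earlier of 84 days after the last Period 1 dose and the first Period 2 dose.
- **Period 2**, by start date: "For Treatment Period 2, TEAEs are those AEs that started on or after the first dose date of study treatment in Treatment Period 2", up to 84 days after the last dose. There is no worsening clause.
- **Entire period:** onset on or after the first dose, or worsening of an event present before it. In these summaries "patients who switched from secukinumab 150 mg to secukinumab 300 mg will appear in both treatment groups".

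Section 2.8 says that safety tables and listings for Period 2 are shown "by treatment group for inadequate responders who are randomized". Protocol section 9.5.2 adds that "All information obtained on adverse events will be displayed by treatment group and patient".

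For other data the SAP takes Week 16 as the reference. Section 2.1.1 states: "For Treatment Period 2, Week 16 assessments will be considered the baseline for all analyses performed during this period". The laboratory shift tables in section 2.8.3 set the "Week 16 laboratory evaluation relative to observed post-Week 16 values in Treatment Period 2".

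Protocol section 7.1 asks for a severity grade, start and end dates and an outcome for each event, with changes in severity reviewed at each visit. Neither document says whether a rise in severity opens a new record.

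**The concern.** Two of three neighbouring definitions mention worsening and the third does not, which reads like an omission. It falls where it would matter most. Every randomised patient has already had 16 weeks of open-label 150 mg, so some events will be ongoing at the first Period 2 dose. If the higher dose aggravated such an event and the site kept a single record, the event would not appear among the Period 2 treatment-emergent events.

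The entire-period tables would not repair this. Their worsening clause is tied to the first study dose, and patients who switched dose are shown under both doses, so those tables do not preserve the randomised comparison. Overall safety and tolerability is a stated objective. Protocol section 3.2 says that dose blinding allows a possible dose-response to be examined for safety as well as efficacy.

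**Working it through.** **Step 1. Apply the three definitions to typical patterns.** Nominal days from the dosing schedule are: first dose day 1, last Period 1 dose (Week 12) day 85, first Period 2 dose (Week 16) day 113, last dose (Week 48) day 337. The Period 1 window closes at the earlier of 85 + 84 = 169 and 112, that is day 112. The Period 2 window closes at 337 + 84 = 421.

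| Event | Period 1 | Period 2 | Entire period |
|---|---|---|---|
| Onset before first dose, worsens in Period 1 | yes | no | yes |
| Onset before first dose, worsens in Period 2, one record | no | **no** | yes |
| Onset in Period 1, worsens in Period 2, one record | yes | **no** | yes (by start date) |
| Onset in Period 1, no worsening | yes | no | yes |
| New record opened when it worsens in Period 2 | no | **yes** | yes |

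The mismatch with the entire-period rule is narrow. The worsening clause concerns only events present before the first study dose, so it matters for the second row alone. In the third row no definition counts the worsening itself: the event enters Period 1 and the entire period by its start date.

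**Step 2. Ask what a worsening clause would add in Period 2.**

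- *A new record is opened.* Its start date lies in Period 2, so it already counts and the loss is 0. Two places make this practice plausible. The ClinicalTrials.gov counting rule in SAP section 2.8.1 provides for "several consecutive TEAEs (irrespective of study treatment causality, seriousness and severity) occurred with the same SOC and PT", and the definition of a serious adverse event in protocol section 7.2.1 includes worsening of something already present.
- *One record is kept.* The items listed in protocol section 7.1 include no date on which severity changed. The worsening then cannot be placed before or after the first Period 2 dose, and the clause could not be programmed from what the documents describe.

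Neither branch shows a case where the clause is both needed and workable.

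**Step 3. Scale.** The documents give no figure for this, so the inputs below are assumptions, apart from 97 per arm (protocol section 9.8, SAP section 3). Patients missed per arm = 97 × share with an event ongoing at Week 16 × share that worsen × share kept on one record.

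- 10% ongoing, 5% worsen, all on one record: 97 × 0.10 × 0.05 = 0.5
- 30%, 20%, all: 97 × 0.30 × 0.20 = 5.8
- 50%, 20%, all: 97 × 0.50 × 0.20 = 9.7
- any shares, none on one record: 0

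A difference between arms changes only if the arms lose unequal numbers. An excess of one patient is 100/97 = 1.03 points, two is 2.06 and three is 3.09.

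As a yardstick, the 95% half-width for a difference is 1.96 × √(2p(1 − p)/97). This gives 3.94 points at p = 2%, 6.13 at 5% and 8.44 at 10%. One patient is therefore 1.03/3.94 = 26%, 1.03/6.13 = 17% or 1.03/8.44 = 12% of the half-width. The SAP plans no between-arm interval for adverse events, so this serves for scale only.

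**The case for a change.** The best case for a change is that single-record practice is quite possible. Protocol section 7.1 has an event followed until it resolves, with severity reviewed along the way, which reads like one event tracked over time. Section 7.2.1.1 has progression of a serious event reported as follow-up to the original report. If worsening always opened a new record, the worsening clauses in the other two definitions would add little. The Week 16 reference for measured data also suggests the same reference for adverse events, and one added clause costs almost nothing.

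Much of this stands. The recording convention is unstated, and a Week 16 severity reference would be a reasonable choice. It is not the only coherent one, however. An event with onset in Period 1 is already treatment-emergent on the same drug, and a start-date rule assigns each event to one period. Adding the clause could count a single event in both periods. The Week 16 passages do not contradict the start-date rule.

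Nor would the events vanish. The planned displays by group and patient still contain them. The SAP also does not state that the summaries by severity, or those of serious events and of events leading to discontinuation, are limited to treatment-emergent events.

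**Conclusion.** No change is needed. The three definitions do differ, and the documents leave the recording convention open. That is a detail which data-entry instructions or programming specifications can settle, and analysts who know the convention can read the Period 2 tables correctly.

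The loss is 0 if worsening opens a new record. Otherwise it cannot be derived: the assumed inputs span 0 to 9.7 patients per arm of 97. Both randomised arms follow the same rule, so a between-arm difference moves only if worsening or its recording differs by dose, which nothing in the documents shows. A material effect is unlikely.

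The SAP's latest update is dated after database lock, so any new table would also be post hoc. The conclusion rests on the case report form holding no separately dated severity change, as the items listed in protocol section 7.1 suggest. If such dates do exist, a Period 2 worsening clause would be feasible, though its benefit would still be undemonstrated.
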